Subjects who discontinue the study prior to the Week 12 visit will be asked to complete the Week 12 visit assessments in the clinic; this will be recorded as an Early Termination (ET1) visit. Subjects who discontinue from the study after Week 12 but prior to Week 24 will be asked to come to the site to complete Week 24 assessments; this visit will be recorded as an ET2 visit.

Safety assessments include BOTE Inflammation Scores, Local Skin Reaction (LSR) scores, adverse event collection, including scarring/keloid and urine pregnancy tests (UPTs). Safety

assessments will be completed at specified visits through Week 12. Adverse events and concomitant medications will be reviewed and updated as needed at each visit through Week 24.

Inflammatory reactions around MC lesions has been associated with imminent resolution of MC (sometimes referred to as “beginning-of-the-end” [“BOTE”] sign). The investigator (or designated evaluator) will assess the presence and overall degree of inflammatory reactions at MC lesions at Baseline (pre-dose) and Weeks 2-12 using the BOTE Inflammation Score (Section 7.1.2.1). BOTE may be associated with itch, but not pain. BOTE is usually asymptomatic, self-limited, localized to individual MC lesions, and does not require discontinuation of study treatment or additional treatment. LSR is generally more diffuse, associated with significant itch or tenderness, may necessitate discontinuation of study treatment, and may need treatment for symptomatic relief (e.g. a topical corticosteroid or topical anesthetic). For very severe LSRs, systemic corticosteroids may be considered (Section 7.2.3 for additional details). Investigators will assess the treatment area at each scheduled visit and use their medical judgement to differentiate between BOTE and LSRs. BOTE Inflammation Score and LSR component scores will be recorded at each visit. When LSRs are clinically significant at the application site, the investigator should report the condition as AE(s).

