6.8 Discontinuation or Withdrawal

6.8.1 Individual Subjects

If at any time during the study the investigator determines that it is not in the best interest of the subject to continue treatment, the subject's treatment will be discontinued. The investigator can discontinue the treatment for a subject at any time if medically necessary. If a subject's treatment is permanently discontinued by the investigator because of an AE, that AE should be indicated as the reason for treatment discontinuation. In this case, the subject is discontinued from the treatment, but still participates in the study and the subject is encouraged to follow the visit schedule and complete all assessments, particularly those at Week 12 and 24.

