7.2.5 Diagnosis of Allergic Contact Dermatitis and Patch Testing

After treatment is reintroduced post-LSR, if a subject experiences a stronger LSR (second LSR event) than the first LSR event, allergic contact dermatitis may be suspected. In order to confirm whether the reaction is allergic contact dermatitis, patch testing should be conducted. If the investigator determines that patch testing is appropriate, he/she should contact the CRO medical monitor to discuss next steps. Patch testing supplies will be provided once requested from the CRO medical monitor. Additional drug product for patch testing may be supplied through IWRS if the currently assigned subject's investigational product was assigned more than 60 days prior to the patch testing date(s) or if the subject had previously returned all their drug product.

Additionally, patch testing should be discussed with the subject/caregiver. If the subject/caregiver consents to patch testing and once the LSR has been completely resolved for a period of 2 weeks and up to 2 months, patch testing will commence. If allergic contact dermatitis is suspected, study drug should be permanently discontinued and an AE of allergic contact dermatitis should be recorded as the reason for discontinuation. Week 12/ET assessments should be completed at the time of discontinuation.

In the event of suspected allergic contact dermatitis developed, photographs may be taken of the affected area(s) and transmitted to the CRO medical monitor for review prior to initiating patch testing. See [Appendix 1](#) for further information.

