7.2.6 Adverse Events

Adverse events will be assessed and collected after the initiation of study drug treatment through the end of the subject's last visit. Treatment-related adverse events and serious adverse events will be followed up until resolution or up to one year after last treatment, whichever occurs earlier.

If a subject's treatment is discontinued by the investigator or the subject because of an AE, that AE should be indicated as the reason for treatment discontinuation. All subjects will be encouraged to remain in the study and to complete all required study visits throughout the 24-week study duration.

If a subject achieves complete clearance at Week 12 or before and experiences new lesions between Week 12 and Week 24, an AE of molluscum contagiosum should be documented to capture this recurrence since there is no lesion count after Week 12.

See [Section 9](#) for additional information regarding adverse events.

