## 7. NOTATION OF TREATMENT GROUPS AND VISITS

### Analysis visits

Baseline is defined as the last non-missing value recorded prior to the first application of study drug. If time is not recorded and the assessment was on the same day as the first application of study drug, then it will be assumed the assessment occurred prior to the application of study drug. The baseline record will have an analysis visit of “Baseline”. If a subject was randomized but not treated, then baseline is defined as the last non-missing value on or before the date of randomization.

For analysis of lesion counts, if there are multiple assessments of differing assessment types (remote vs in-clinic) within a given window, then the in-clinic lesion count will be used for analysis. For all evaluations of all parameters, assessments will be analyzed according to the visit at which they occurred (i.e., per the eCRF visit label). In order to account for the fact that the Week 12 and Early Termination visits are collected on the same eCRF in the database, a check against the Study Exit form will be made to determine if the visit is a Week 12 or an Early Termination Visit. If the visit is an Early Termination visit, then the visit will be mapped according to the table below. If there is no corresponding Study Exit form on the same date, then it will be considered a Week 12 visit. If there is no assessment in a given visit, then the following visit windows will be applied to determine if an unscheduled visit may be used:

Visit	Analysis Visit	Target Study Day	Study Day Analysis Window
Week 2 (±3 days)	Week 2	15	Day 12 to 22
Week 4 (±5 days)	Week 4	29	Day 23 to 43
Week 8 (±5 days)	Week 8	57	Day 44 to 71
Week 12 (±5 days)	Week 12	85	Day 72 to 98
Week 16 (±7 days)	Week 16	113	Day 99 to 126

Visit	Analysis Visit	Target Study Day	Study Day Analysis Window
Week 20 ( $\pm 7$ days)	Week 20	141	Day 127 to 154
Week 24 ( $\pm 7$ days)	Week 24	169	Day 155 to 182

Days are measured from the date of randomization. Study days corresponding to measurements are calculated as:

- Assessment date – date of randomization + 1, if assessment date is on or after the date of randomization.
- Assessment date – date of randomization, if measurement date is before the date of randomization.

In the event of multiple unscheduled records falling in the same analysis window, the assessment which is closest to the target study day will be chosen for analysis.

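### Protocol 7.2.5 attaches the Week 12/ET assessments to a drug stop for suspected allergic contact dermatitis, so an early count can be analysed as Week 12 or the true Week 12 count can be lost

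*Protocol*

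**What the plan says.** Protocol 7.2.5 covers a second, stronger local skin reaction after drug has been reintroduced. It states "If allergic contact dermatitis is suspected, study drug should be permanently discontinued" and then "Week 12/ET assessments should be completed at the time of discontinuation". What is discontinued there is study drug, not study participation.

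The rest of the protocol handles follow-up after a drug stop differently:

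- Section 6.8.1, on a permanent stop for an AE: "the subject is discontinued from the treatment, but still participates in the study and the subject is encouraged to follow the visit schedule". It adds that the subject should "complete all assessments, particularly those at Week 12 and 24".
- Section 7.2.6: "All subjects will be encouraged to remain in the study and to complete all required study visits throughout the 24-week study duration".
- Section 4.1 ties the early visit to study exit: "Subjects who discontinue the study prior to the Week 12 visit will be asked to complete the Week 12 visit assessments in the clinic", recorded as ET1. Section 6.8.3 does the same.
- Section 9.4, on another kind of drug stop (pregnancy), has the subject continue visits through Week 24.

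SAP section 7 (Analysis visits) says that the Week 12 and early termination visits share one eCRF. They are told apart by checking the Study Exit form. An early termination visit is mapped to a window by study day. Otherwise: "If there is no corresponding Study Exit form on the same date, then it will be considered a Week 12 visit".

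**The concern.** Section 7.2.5 applies a study-exit visit to subjects who are meant to stay. They are expected to remain under observation: 7.2.5 and Appendix 1 start patch testing only once the reaction has been resolved for 2 weeks to 2 months.

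A site that follows 7.2.5 completes the Week 12/ET assessments, including the lesion count, whenever the drug stops. That may be weeks before Day 85 and during a strong skin reaction. The primary endpoint and two of the four secondary endpoints are read from the Week 12 lesion count. At stake is whether that count is the true Week 12 value, an earlier value carrying the Week 12 label, or missing. The trigger is a reaction to the applied product, so any loss is likely to be related to treatment. It is also avoidable.

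**Working it through.** **1. What happens to the primary endpoint under each way of applying the text**

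| Site action after the drug stop | Handling under the documents | Week 12 result |
|---|---|---|
| Subject exited the same day, before Day 72 | SAP section 7 maps the ET form to an earlier window (the Week 12 window is Day 72 to 98) | Non-response (Protocol 10.3.1, SAP 10.4) |
| Subject stays; no Study Exit form on that date; no later count | SAP section 7 takes the form as Week 12, whatever its study day | The early count is analysed as Week 12 |
| Subject stays; Day 85 count also taken | Two records carry the Week 12 label; the tie rules cover only remote versus in-clinic counts and multiple unscheduled records | Not defined |

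In the second row the value is not missing. The missing-data analyses in SAP 10.4 (multiple imputation, last assessment, patient-reported status) therefore would not reach it.

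**2. Is the effect likely to differ by arm?** (Protocol 2.1.4.2, Tables 2 to 4)

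- TEAEs leading to a drug stop, both trials: SB206 (7 + 17)/(235 + 237) = 24/472 = 5.1%; vehicle (1 + 1)/(116 + 117) = 2/233 = 0.9%. Fisher p = 0.005.
- Contact dermatitis, NI-MC302: SB206 6/237 = 2.5%; vehicle 0/117. Fisher p = 0.18.
- Application site dermatitis, both trials: SB206 (5 + 11)/472 = 16/472 = 3.4%; vehicle (1 + 1)/233 = 2/233 = 0.9%.

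All three point to an excess on SB206. None of them counts the 7.2.5 trigger.

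**3. The plan's own power**

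Inputs (Protocol 10.2.1): 425 per arm, 20% versus 29.5%, two-sided alpha 0.05, stated power 90%.

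- Pooled rate = (0.20 + 0.295)/2 = 0.2475; SE under the null = √(0.2475 × 0.7525 × 2/425) = 0.0296.
- SE under the alternative = √((0.20 × 0.80 + 0.295 × 0.705)/425) = 0.0294.
- Power = Φ((0.095 − 1.96 × 0.0296)/0.0294) = 89.6%. The stated figure reproduces.

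**4. Upper bound on the loss**

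Let f be the share of SB206 subjects affected and r their true Week 12 clearance rate. Both are assumptions. Suppose every affected subject is scored as not clear and vehicle loses nothing. The SB206 rate becomes 0.295 − f × r, and power is recalculated with the formula in step 3.

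Values of f: 6/472 = 1.3% (no contact dermatitis in NI-MC301); 10/472 = 2.1% (the most that could be unseen there, since Table 3 lists only terms at 2% or more and 4/235 = 1.7% falls below that); 6/237 = 2.5% (NI-MC302 alone). Values of r: 20% (planned vehicle rate) and 29.5% (planned SB206 rate).

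| f | SB206 subjects of 425 | r | Points lost (f × r) | Difference left | Power |
|---|---|---|---|---|---|
| 1.3% | 5.4 | 20% | 0.25 | 9.25 | 88.0% |
| 1.3% | 5.4 | 29.5% | 0.37 | 9.1 | 87.2% |
| 2.1% | 9.0 | 20% | 0.42 | 9.1 | 86.9% |
| 2.1% | 9.0 | 29.5% | 0.62 | 8.9 | 85.5% |
| 2.5% | 10.8 | 20% | 0.51 | 9.0 | 86.3% |
| 2.5% | 10.8 | 29.5% | 0.75 | 8.75 | 84.5% |

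If only half the counts are lost, the first row becomes 0.13 points and 88.8%.

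**The case against.** The strongest reply is that the two instructions are compatible. Section 7.2.5 does not say that the subject leaves the study or that the Day 85 visit is dropped. Sections 4.1, 6.8.1 and 7.2.6 all tell sites to keep the subject. A site can assess at the drug stop and count again at Week 12. That stands, and it is why loss is possible rather than certain. It does not dispose of the point, because a site that does both still produces two records labelled Week 12, with no rule for choosing between them.

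A reader might infer that the site would have no Week 12 form left for Day 85. The documents do not say this. They say the two visits share one eCRF, not that it can be entered only once, and the eCRF itself is not available.

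A reader might also infer that the affected group would arise almost only on SB206. That goes too far: 6/237 against 0/117 is compatible with chance, vehicle had application site dermatitis too, and the trigger itself is not counted. An excess on SB206 is the reasonable expectation, mainly from the drug-stop figures.

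Finally, scoring early study dropouts as non-responders is pre-specified. For subjects who are exited, the sensitivity analyses in SAP 10.4 and 11.1 give some cover. This stands for that case only; an early count taken as Week 12 gets no such cover.

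**Conclusion.** The inconsistency is real and should be resolved. Read with SAP section 7, Protocol 7.2.5 can put an early count into the primary endpoint, leave the Week 12 count missing, or create two competing Week 12 records.

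The size is modest. The upper bound is about 0.25 to 0.75 of the 9.5 planned points, with power falling from 89.6% to about 88% to 85%. It rests on assumed values of 1.3% to 2.5% affected on SB206 and 20% to 29.5% true clearance, with none affected on vehicle and every count lost. It would be tempting to take the 2.5% and 29.5% case as the expected loss. The documents do not support that: the 2.5% comes from one of two trials and exceeds the pooled maximum of 2.1%, and it counts a reported AE term, not the 7.2.5 trigger. The effect is smaller if only some counts are lost. Part of it may already be in the planning rates, since the two earlier trials also scored missing Week 12 counts as non-response.

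The likely direction is against SB206, because an early count is less likely to be zero. The problem costs power and precision and does not raise the false-positive risk.

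**What to change.** Reconcile 7.2.5 with 6.8.1 and 4.1 on follow-up only, leaving the rule for stopping drug untouched:

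- In 7.2.5, record the assessments made at the drug stop as an unscheduled (end-of-drug) visit.
- Keep the subject on the visit schedule, with the Week 12 lesion count at Day 85 ±5.
- Use the Week 12/ET1 form early only when the subject leaves the study.
- In SAP section 7, state that an early Week 12/ET form without study exit is mapped by its study day and is not taken as Week 12.

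The cost is one sentence in each document and a memo to sites. The visits are already in the Schedule of Assessments, and neither the sample size nor the stated power changes.

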7.2.6 Adverse Events

Adverse events will be assessed and collected after the initiation of study drug treatment through the end of the subject's last visit. Treatment-related adverse events and serious adverse events will be followed up until resolution or up to one year after last treatment, whichever occurs earlier.

If a subject's treatment is discontinued by the investigator or the subject because of an AE, that AE should be indicated as the reason for treatment discontinuation. All subjects will be encouraged to remain in the study and to complete all required study visits throughout the 24-week study duration.

If a subject achieves complete clearance at Week 12 or before and experiences new lesions between Week 12 and Week 24, an AE of molluscum contagiosum should be documented to capture this recurrence since there is no lesion count after Week 12.

See [Section 9](#) for additional information regarding adverse events.

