2.1.2.1 Administration Regimen

Subjects will apply treatment once daily for up to 12 weeks to all active lesions identified at Baseline and new lesions that arise during treatment. If the investigator determines all lesions are cleared at a visit, the treatment may stop. If treatment is stopped due to clearance, subjects will continue regularly scheduled visits through Week 24 and study drug will be dispensed in case of lesion recurrence between study visits. Prior to Week 12, if lesions recur or new lesions appear

after the subject has cleared, treatment should be resumed. No further treatment will occur after Week 12.

An increase in the number of MC lesions (with or without inflammatory reaction) during the early treatment period is often observed. It is important to instruct the subject/caregiver to treat the new lesions as well as the existing lesions.

Each dose will consist of berdazimer gel or vehicle gel with hydrogel thoroughly mixed together by the subject or caregiver on a supplied dosing guide and applied to the individual lesions. Periocular lesions will be treated if the lesions are at least 2 cm from the edge of the eye. If a subject has more than 20 MC, a second dose of berdazimer gel or vehicle gel with hydrogel can be prepared to ensure appropriate coverage of all lesions.

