6.7.7 Visit 6/Week 12/ET (Day 85 ±5 days) (In-clinic Visit)

The following procedures must be performed and recorded at the Week 12/ET visit.

1. Obtain pregnancy test and evaluate results, as applicable.
2. Perform BOTE Inflammation Score.
3. Perform Local Skin Reaction Assessment.
4. Perform lesion counts and update lesion map with location for any new lesions.
5. If previously cleared, assess for subject recurrence of MC.
6. Perform scarring/keloid assessment; if present, document location on lesion map and record as an AE.

7. Perform a brief physical examination.
8. Complete Investigator Global Severity Assessment and Investigator Global Impression of Change Assessment.
9. Complete Subject Global Severity Assessment and Subject Global Impression of Change Assessment.
10. Subject/caregiver administer final dose of study drug from previously dispensed kit only if lesions are present.
11. Weigh returned study drug and review study compliance.
12. Collect and record AE information for AEs reported.
13. Update concomitant medication information and confirm if any new occurrences of MC were reported in the subject's household.
14. Review interview procedures with the subject/caregiver and obtain documented ICF/assent.

Note: Follow up interviews will be performed with a subset of subjects that complete Week 12. Consent will be obtained during the Week 12 visit, and the follow up interview will be performed with the subject/caregiver at a later date.

**6.7.8 Visit 7/Week 16 and Visit 8/Week 20 (Day 113 ±7 days; Day 141 ±7 days)
(Telephone Contact)**

The following procedures must be performed and recorded at the Week 16 and Week 20 visits. It is expected that these visits should be done by telephone.

1. Collect and record information for new and ongoing AEs, including recurrence of MC.
2. Confirm household MC status (any new cases in household members since last visit).
3. Update concomitant medication information.

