6.7.9 Visit 9/Week 24 (Day 169 ± 7 days) (In-clinic Visit)

The following procedures must be performed and recorded at the Week 24 visit.

1. Perform scarring/keloid assessment; if present, document location on lesion map and record as an AE.
2. Complete Investigator Global Severity Assessment and Investigator Global Impression of Change.
3. Complete Subject/Caregiver Global Severity Assessment and Subject Global Impression of Change.
4. Collect and record information for new and ongoing AEs, including subject recurrence of MC.
5. Confirm household MC status (any new cases in household members since last visit visit).
6. Update concomitant medication information.

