## 6. GENERAL ANALYSIS CONSIDERATIONS

The statistical analyses will be reported using summary tables, listings, and figures (TLFs). The International Council for Harmonisation (ICH) numbering convention will be used for all TLFs. Unless otherwise noted, all statistical testing will be two-sided and will be performed at the 0.05 significance level. Tests will be declared statistically significant if the calculated  $P$ -value is  $\leq 0.05$ .

Continuous variable summaries will include the number of subjects ( $n$ ) with non-missing values, mean, standard deviation (SD), median, minimum, and maximum. Other statistics such as quartiles, confidence intervals (CIs), and number of missing values may be added as appropriate.

Categorical variable summaries will include the frequency and percentage of subjects who are in the category or each possible value. In general, the denominator for the percentage calculation will be based upon the total number of subjects in the study population within each treatment group, unless otherwise specified. The denominator for by-visit displays will be the number of subjects in the relevant study population with non-missing data at each visit.

All summary tables will be presented by treatment group. Baseline summaries will also include an overall summary column.

Individual subject data obtained from the eCRFs and any derived data will generally be presented by subject in data listings. Additionally, a listing of the subjects requiring a narrative because they experience one of the following events: serious adverse event, death, discontinued the study due to an AE, hypertrophic or keloid scarring, unresolved scars, or LSR suggestive of allergic contact dermatitis will be presented.

A separate report for the results from the study exit interview will be created.

The analyses described in this plan are considered a priori, in that they have been defined prior to breaking the blind.

Any analyses performed subsequent to breaking the blind will be considered post hoc and exploratory. Post hoc analyses will be labeled as such on the output and identified in the clinical study report.

All analyses and tabulations will be performed using SAS® software Version 9.4 or higher. Tables, listings, and figures will be presented in RTF format.

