### 11.3 Exploratory Analyses

Since the within-household correlation is expected to be small, the change and percent change from Baseline in the number of treatable MC at Weeks 2, 8 and 12 will be analyzed using a repeated measures mixed model for the respective visits with the same covariates as the primary model together with visits and treatment by visit; an unstructured covariance matrix will be utilized. If the calculation of the percent change from baseline is influenced by outliers with calculated values  $>100\%$ , then the influence of outliers will be avoided for analysis by censoring them so that all values were in the range of  $-100\%$  to  $100\%$ . If the model fails to converge, then other correlation structures will be explored.

The exploratory endpoints based on the proportion of subjects achieving complete clearance (at Weeks 2 and 4) or 75% (at Weeks 2, 4, 8, and 12) or 90% (at Weeks 2, 4, and 8) reductions will be analyzed in the same manner as the primary endpoint.

Likewise, the proportion of subjects achieving a lesion count of 0 or 1 of all treatable MC at Weeks 2, 4 and 8 will be analyzed in the same manner as the primary endpoint.

Since the within-household correlation is expected to be small and time to first complete clearance of all MC is exploratory, it will be analyzed using Kaplan-Meier methods. The number and percentage of subjects achieving complete clearance, number and percentage of censored subjects, and Kaplan-Meier estimates of first quartile, median, and third quartile will be summarized by treatment group. Differences in Kaplan-Meier curves between the treatments will be tested for significance using a stratified log-rank test.

The proportion of subjects who have a recurrence of MC after the first visit at which complete clearance was observed will be summarized.

The subject-reported spread of MC to household members not in the study will be summarized descriptively including a breakdown of whether or not there was any spread and then a breakdown of the amount of spread within the household at each visit at the household level.

A shift table comparing the baseline global severity assessment to each scheduled postbaseline assessment will be presented by subject and investigator. The Investigator and Subject Global Impression of change will be summarized descriptively.

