#### 13.1 Adverse Events

Adverse event summaries restricted to treatment-emergent AEs (TEAEs) will include those AEs that occurred any time on or after the first in-clinical application of study drug through the last application of study drug and those existing AEs that worsened during this same period. If it cannot be determined whether the AE is treatment emergent due to a partial onset date, then it will be counted as such; see Appendix A for the imputation of missing dates algorithm. Post treatment AEs will include those AEs that occurred after the last application of study drug. Verbatim terms in the eCRFs will be mapped to preferred terms and system organ classes using the MedDRA Version 23.0 or later.

Each AE summary will be displayed by treatment group. Summaries that are displayed by system organ classes and preferred terms will be ordered by descending order of incidence in SB206 treatment group of system organ class and preferred term within each system organ class. Summaries of the following types will be presented:

- Overall summary of TEAEs and post treatment AEs that contain an overview of each item below.

- Subject incidence of TEAEs with total number of unique TEAEs and post treatment AEs with total number of unique post treatment AEs by MedDRA system organ class and preferred term.
- Subject incidence of TEAEs and post treatment AEs by MedDRA system organ class, preferred term, and maximum severity. At each level of subject summarization, a subject is classified according to the maximum severity if the subject reported 1 or more events. Adverse events with missing severity will be considered severe for this summary.
- Subject incidence of TEAEs by MedDRA system organ class, preferred term, and closest relationship to study drug (Related/Not Related). Related AEs are those reported as “Definite,” “Probable,” or “Possible,” and unrelated AEs are those reported as “Unlikely” or “Unrelated.” At each level of subject summarization, a subject is classified according to the closest relationship if the subject reported 1 or more events. Adverse events with a missing relationship will be considered related for this summary.
- Subject incidence of serious TEAEs with total number of unique serious TEAEs and post treatment serious AEs with total number of unique post treatment serious AEs by MedDRA system organ class and preferred term.

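### Recurrence after Week 12 must be recorded as an AE only in subjects who had cleared, but the post treatment AE tables divide by all Safety subjects, so the rate depends partly on the efficacy result

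*Protocol*

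**What the plan says.** Protocol 7.2.6 sets a condition on the subject's earlier response: "If a subject achieves complete clearance at Week 12 or before and experiences new lesions between Week 12 and Week 24", then "an AE of molluscum contagiosum should be documented to capture this recurrence since there is no lesion count after Week 12". The follow-up contacts use the same route. At the Week 16 and Week 20 calls (Protocol 6.7.8) sites are to "Collect and record information for new and ongoing AEs, including recurrence of MC", and at Week 24 (Protocol 6.7.9) to "Collect and record information for new and ongoing AEs, including subject recurrence of MC". The schedule of assessments lists no lesion count after Week 12.

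These events fall outside the treatment period, because Protocol 2.1.2.1 states that "No further treatment will occur after Week 12". SAP 13.1 then classifies them: "Post treatment AEs will include those AEs that occurred after the last application of study drug". They enter the overall, SOC/preferred term and severity tables for post treatment AEs (14.3.1.1.2, 14.3.1.2.2, 14.3.1.3.2), all on the Safety Population. SAP 8 defines that population as everyone with at least one application, cleared or not. Under SAP 6 the general denominator is "based upon the total number of subjects in the study population within each treatment group, unless otherwise specified", and SAP 13.1 specifies nothing different for this event.

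There is also an exploratory recurrence endpoint. SAP 11.3 says only: "The proportion of subjects who have a recurrence of MC after the first visit at which complete clearance was observed will be summarized". SAP 10.1 defines it by a lesion count above 0 after an earlier count of 0.

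**The concern.** A subject has to clear before the written instruction applies. A subject whose lesions persist or multiply after Week 12 is covered by no such instruction. The arm that clears more subjects therefore has more subjects for whom the AE is required, while the denominator stays at the full arm. The resulting percentage is the product of two quantities, the clearance rate and the relapse rate among those who cleared. A reader of a post treatment AE table would normally take it as a measure of late harm.

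Two things are at stake. First, the overall and SOC rows of the post treatment tables mix an efficacy-dependent event with ordinary late AEs. Second, both the Protocol (4.1) and the SAP (4) name recurrence as a purpose of the Week 24 visit, yet the recurrence endpoint rests on lesion counts whose schedule ends at Week 12. No planned table then gives later recurrence among the subjects who had cleared.

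**Working it through.** **Inputs.** Planned clearance at Week 12 is 29.5% on SB206 and 20% on vehicle, with 425 per arm (Protocol 10.2.1, SAP 5). Integrated clearance in the two earlier phase 3 studies was 27.9% versus 20.9% (Protocol 2.1). The relapse risk r among cleared subjects between Weeks 12 and 24 is not in the documents. It is an assumption here, varied from 5% to 40% and first taken as equal in both arms. All 425 per arm are assumed dosed. Week 12 clearers stand in for everyone who cleared by Week 12, a somewhat larger group.

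**The plan's own figure.** For a two-sided 0.05 test of 20% versus 29.5% with 425 per arm, the pooled rate is 0.2475. The null standard error is √(2 × 0.2475 × 0.7525 / 425) = 0.0296. The alternative standard error is √((0.20 × 0.80 + 0.295 × 0.705) / 425) = 0.0294. Power = Φ((0.095 − 1.96 × 0.0296) / 0.0294) ≈ 0.896, which agrees with the stated 90%. The clearance rates used below are therefore those on which the trial was sized.

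**Subjects covered by the instruction.** SB206: 0.295 × 425 = 125.4. Vehicle: 0.20 × 425 = 85.0. Ratio: 125.4 / 85.0 = 1.475.

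**What the post treatment tables would show with equal relapse risk.** Expected subjects = 425 × clearance × r; table percentage = clearance × r.

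| Assumed r, both arms | SB206 | Vehicle | Rate among cleared |
|---|---|---|---|
| 5% | 6.3 (1.5%) | 4.3 (1.0%) | 5% vs 5% |
| 10% | 12.5 (3.0%) | 8.5 (2.0%) | 10% vs 10% |
| 20% | 25.1 (5.9%) | 17.0 (4.0%) | 20% vs 20% |
| 30% | 37.6 (8.9%) | 25.5 (6.0%) | 30% vs 30% |
| 40% | 50.2 (11.8%) | 34.0 (8.0%) | 40% vs 40% |

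The ratio of the all-subject rates is 1.475 in every row. At the earlier integrated rates it is 27.9 / 20.9 = 1.33.

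**Unequal relapse risk.** Let the risk on SB206 be k times that on vehicle. The all-subject rates are equal when 0.295 × k = 0.20, so k = 20 / 29.5 = 0.68. At the integrated rates, k = 20.9 / 27.9 = 0.75. With vehicle risk at 20%:
- k = 0.8 gives 0.295 × 0.8 × 20% = 4.7% versus 4.0%. A lower relapse risk on SB206 appears as a higher event rate.
- k = 0.5 gives 0.295 × 0.5 × 20% = 3.0% versus 4.0%. The direction is right but the relative size is not.

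**The case against.** The strongest reply is that little depends on these tables. Protocol 10.3.4 rules out inferential statistics for safety endpoints, so no test or study decision changes. Post treatment AEs are tabulated apart from TEAEs, and molluscum contagiosum would be visible as its own preferred term. A reader could combine the clearance counts in Table 14.2.1.1 with Listing 16.2.7.4 to approximate the rate among cleared subjects. Both global severity assessments are repeated at Week 24 in everyone, with a category for no disease. The gap is also small in absolute terms: at 10% relapse it is about 4 subjects per 425.

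All of this stands, and it limits the weight of the point. It does not remove it. The overall and SOC rows still combine these events with others. The Week 24 severity scores describe current status in all subjects, not relapse in those who had cleared.

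A reader might infer that an uncleared subject cannot have this AE at all. The text does not go that far. Protocol 9.1 defines an AE broadly, and a site may record worsening disease in a subject who never cleared; it is simply not instructed to. If many sites did so, the imbalance would shrink.

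A reader might also infer that the recurrence table (14.2.3.7) will show excess recurrence on SB206. That is not established. The SAP 6 rule is a general default, the endpoint is worded as recurrence after clearance, and the table shells are in a separate file. Analysts may well use cleared subjects. The supportable statement is that the denominator is not stated.

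**Conclusion.** The point holds as a limited reporting problem. The written AE instruction covers only subjects who had cleared, the planned denominator is all Safety subjects, and no planned table relates recurrence after Week 12 to the subjects at risk of it. At the planned clearance rates, with equal relapse risk and AEs recorded only as instructed, the all-subject rate on SB206 is inflated by a factor of 1.475 (1.33 at the earlier integrated rates).

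It would be tempting to conclude that SB206 will look less safe the better it works. The documents do not support that. The direction depends on an unknown relapse risk, and the excess is gone once the risk on SB206 is about 0.68 of vehicle or lower. TEAE summaries stop at the last application and are untouched, as are the primary and secondary tests. Only the three post treatment AE tables are affected. This is an inexpensive improvement, not a threat to the trial's conclusions.

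**What to change.** Amend the SAP before the Week 12 unblinding. SAP 6 breaks the blind while follow-up continues and labels anything added afterwards post hoc, so a denominator chosen later would be chosen with clearance by arm already known.

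- SAP 13.1: leave the recurrence AEs in the post treatment tables and listings. Add an overall post treatment AE count that excludes the molluscum contagiosum preferred term, next to the planned count that includes it.
- SAP 13.1: add a descriptive row for recurrence after Week 12, with subjects who had reached complete clearance by Week 12 as the denominator.
- SAP 11.3: state that Table 14.2.3.7 uses subjects with a prior lesion count of 0 and a later count.

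The cost is one or two table rows and a few SAP sentences, with no new data. The drawback is that the cleared-subject comparison conditions on an outcome after randomization. It is not a randomized comparison and should be labelled descriptive.
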